13.0 STUDY MANAGEMENT

13.1 Protocol deviations and violation(s)

A protocol deviation will be any failure to adhere to the defined procedures or intervention plans outlined in the protocol version approved by Scientific Ethics Review Unit (SERU) and Oxford Tropical Research Ethics Committee (OxTREC). A protocol violation is any planned or inadvertent changes that may impact safety of study participants, affect integrity of the study data and/or affect study participants willingness to participate in the study previously approved by the SERU or OxTREC. Any unforeseen and unavoidable deviations from the protocol will be documented and filed in a protocol deviation folder, with explanation and reported to the relevant ethical and regulatory authorities during the annual reports to ethical review boards while violations will be reported immediately.

13.2 Discontinuation of the study

The study in its entirety may be discontinued prematurely by the Sponsor, or the Ethics Committee with oversight responsibilities at any time. All arms of the study may be discontinued by the sponsors in the event of the following but not limited to:

- i. occurrence of an unanticipated health or technological problem
- ii. evidence of serious and/or continuing noncompliance.

iii. safety or human rights concerns raised by the ethics committees in Kenya and Oxford.

13.3 Withdrawal of Study Participants

Participant may opt to withdraw from the study at any point. The study team may withdraw them from the study if it is established that they are not accessing SMS, have missed two of the follow up periods, have stopped taking anti-seizure medications following advice by the attending clinician or those who have emigrated or died. Participants may terminate their participation prematurely, or have their participation terminated by the Investigator

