An intervention that utilises a mobile messaging service could serve to remind patients with epilepsy (PWE) to take their medication. This has not been undertaken before and is now feasible because of greater mobile network coverage in rural areas in Kenya and increasing mobile phone ownership and usage in these areas. Use of SMS is more widespread in antiretroviral and antimalarial adherence studies in Africa and has shown great promise in improving adherence to medication and consequently, outcomes. This study will further test the evidence to support the use of graphics in impoverished semi-literate communities such as the study sites to convey health-related messages. These multi-media messages will be designed in a simple format that is compatible with both basic phones and smart phones. However, since the display characteristics of basic phones and smart phones may differ, we will document the type of phone used by the participant and this will be taken into consideration during the analyses and interpretation of findings. It is unclear whether either one of these interventions will improve adherence in a rural population or informal settlements with high rates of illiteracy.

A two-way SMS platform will be implemented such that PWE participating in the study will be able to receive messages from the study team and send messages to the study team via normal text or using an unstructured supplementary service data (USSD) prompt at no cost to the PWE. The SMS platform will also be able to send delivery reports to the study team if the message is delivered to the intended user and a read report once the message is opened by the intended user. During planned follow up visits, we will also check for any issues regarding receiving messages, disruptions in the network service provider or electricity, change of phone number, change of handsets and whether caregivers relay messages to the PWE in the case that they are the ones receiving the SMS on behalf of the PWE. Those who do not relay messages will be encouraged to do so and changes in phone numbers will be updated. Since this is meant to be a pragmatic trial that can be rolled out in a sustainable fashion throughout resource-poor settings, challenges are to be expected and will be taken into consideration when interpreting the findings.

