Both text (SMS) and picture messaging (MMS) demonstrate strong potential as tools for healthcare improvement for several reasons: these are accessible on almost every model of mobile phone even basic phones; the cost of transmission is relatively low; neither require great technological expertise, and the transmission of brief health-related messages are widely applicable to a variety of health behaviours and conditions. However, since reading text messages requires some level of literacy, we will compare texts versus graphic messages and the impact on ASM adherence. The messaging service also has the advantage of being asynchronous because it can be accessed at any time that is personally convenient. Use of SMS is more widespread in antiretroviral and antimalarial adherence studies in Africa. This study will further test the evidence to support the use of graphics in impoverished semi-literate communities to convey health-related messages. Improved adherence may subsequently improve quality of life among people with epilepsy, reduce accidental injuries, psychiatric comorbidities, and premature mortality. Nevertheless, it is unclear whether either one of these interventions will improve adherence in a rural population with high rates of illiteracy.

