7.0 TRIAL DESIGN

7.1 Overall Study Design

This study will follow a single-blinded randomized controlled trial design. Participants will be randomly selected from a database of over 3500 PWE. The selected participants will be invited to the clinic for screening against the eligibility criteria and enrolment into the study. The study sample will consist of 1,200 people with epilepsy in each site. Out of the 1200 PWE, there will be 900 participants in the intervention arm (300 receiving text SMS, 300 receiving graphic SMS, 300 receiving both text and graphic) and 300 in the control arm (non-epilepsy related SMS) (Figure 1). The participants will be aware of the intervention status, but the researcher and clinical staff will not. All participants will receive an SMS (cases to

encourage adherence and controls will receive non-epilepsy related messages) for comparability and to reduce the risk of disclosing the blind during follow up visits. Participants will be encouraged to not disclose the content of their messages during follow up visits. As a secondary outcome, ASM-related ADRs including neurological and psychiatric ADRs, will be documented for all participants on ASMs, and where possible, related to type (s) of ASM used.

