8.0 DESCRIPTION OF THE INTERVENTION

8.1 Intervention

The intervention will be a short message service (SMS) reminder sent to the mobile phones of participants in the intervention group reminding them to take their anti-seizure medications. This will be a behavioural intervention with no investigational medicinal product. Each SMS (text or graphic or both) adherence message will be 120–140 characters long. To increase the probability that that the PWE or family member will read the messages and support family members with epilepsy, message will be randomly complemented with a quote (up to 60 characters long) and unrelated to epilepsy treatment, but designed to be motivating, entertaining, or merely attention-getting. This motivational element was used with success in the health workers adherence to antimalarial guideline studies. The graphics will be hand drawn by a local illustrator and the accompanying text of no more than 15 characters will be scanned and sent as low-resolution jpeg files, suitable for the MMS format that is compatible with basic phones.

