An automated computer system will be used to generate standard text messages to remind patients to take their ASMs at the prescribed time and to refill their prescriptions. The system will have an algorithm to check time, send the text message and generate a delivery report. Participants will be able to send replies to the messages, either via text or USSD codes at no cost. A three-step verification SMS system will be designed to send a delivery report (which shows if the message has been delivered) and a read receipt (which shows if the message has been opened) back to the service provider and study team and each message will prompt for a USSD or text response at no cost to the participant asking if they have read the message. The participants in the no-intervention group will receive routine care, including clinic appointment for review of symptoms and medication review and refills and routine electroencephalography (EEG) recordings. For comparability, the control group will receive

public health promotion messages (not related to epilepsy) such as use of bednets. All other data will be collected in the case report forms during scheduled follow up visits at the clinic.

(iv) Anti-seizure medication (ASM)-related adverse drug reactions (ADRs)

Cognisant that this trial doesn't involve administration of medicinal products, we would like to document and describe reported drug-related adverse events of ASM as part of routine care. These data have not been previously systematically documented in relation ASM use in the study population. ASM-related adverse drug reactions will be documented and graded according to Common Toxicity Criteria for Adverse Events (CTCAE), including date and time of onset, severity, and relationship to drug administration. Standardised assessment will be used to measure various emerging ADRs. These data will be used in a secondary analysis to investigate the association of toxicity with ASM concentrations. Any side effects of ASMs will be documented for all the participants and correlated with type of ASM used and where possible, the ASM levels in blood. This will include abnormalities during pregnancy such as congenital abnormalities/birth defects since certain ASMs such as sodium valproate are known to be teratogenic. This information will be collected into case review forms at baseline and during follow up visits.

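### Participants can be withdrawn from the study for not accessing SMS, so outcomes may be missing for a reason linked to the assigned message

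*Combined protocol and SAP*

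**What the plan says.** Section 13.3 (Withdrawal of Study Participants) states: "The study team may withdraw them from the study if it is established that they are not accessing SMS". The same sentence lists those who "have missed two of the follow up periods" as a further ground. It does not separate stopping messages from ending follow-up, and it does not say how non-access is established.

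Section 9.2.6 describes what could establish it: a delivery report, "a read receipt (which shows if the message has been opened) back to the service provider and study team", and a reply prompt with each message. All of these arise after randomisation.

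The arms differ in what has to be accessed. Section 5.3 says "since reading text messages requires some level of literacy, we will compare texts versus graphic messages". Section 8.1 says graphics are sent as "low-resolution jpeg files, suitable for the MMS format that is compatible with basic phones". Section 5.2 adds: "since the display characteristics of basic phones and smart phones may differ, we will document the type of phone used by the participant". Controls also receive messages (section 7.1), so the rule can apply in all four arms.

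On intent, section 5.2 says "Since this is meant to be a pragmatic trial that can be rolled out in a sustainable fashion", and goes on to expect difficulties and to weigh them in interpretation. Section 12.2.2 names full analysis, intention-to-treat and per-protocol sets without defining them, and states no method for missing outcomes. Tracing in section 9.3 covers people who miss visits, not people the team has removed.

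**The concern.** Whether a participant accesses the messages is a consequence of randomisation and part of what the trial tests. If non-access ends study participation, later blood levels and MMAS-8, including those at month 12, are not provided for. An intention-to-treat analysis then has nothing observed to analyse for these people.

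Two things are at stake. First, if withdrawal rates differ by arm, or the people withdrawn differ in adherence by arm, the comparison is biased even with no true effect. The text v graphic comparison is the most exposed, because the formats make different demands on the reader and the handset. Second, even with balanced withdrawal, removing non-accessors moves the estimate from the effect in everyone randomised towards the effect in those who access the messages. That sits badly with a trial described as pragmatic.

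A smaller, separate point concerns missed visits. Follow-up is at months 3, 6 and 12. Someone who misses the first two may be withdrawn before month 12 although still reachable, whereas section 9.3 counts a person as lost only after three calls and a home visit.

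**Working it through.** **Inputs from the plan.** 300 per arm per site; adherence gap of 62% in Kilifi, so 38% adherent; 10% attrition and design effect 1.5, with 20% loss also mentioned (all section 12.1); pooled gap of 79.1% by optimal drug levels, so 20.9% adherent (section 5.1). The plan gives no non-access rate, so all withdrawal rates, and adherence in those withdrawn, are assumed.

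**The plan's own power figure.** Effective n per arm = 300 × 0.90 / 1.5 = 180. Reading the 50% improvement as relative (38% to 57%) and assuming two-sided 5% alpha, power is 95.4%, which matches the stated 95%. At 20% loss, n = 300 × 0.80 / 1.5 = 160 and power is 92.9%. The attrition allowance therefore covers precision. It does nothing for selective loss.

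**Month 12, no true effect, available cases.** With overall adherence p, share withdrawn f and adherence a in those withdrawn:

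observed rate = (p − f·a) / (1 − f)

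For p = 0.38, a = 0.20, f = 0.20: (0.38 − 0.04)/0.80 = 0.425. For f = 0.10: (0.38 − 0.02)/0.90 = 0.400. RR = 0.425/0.400 = 1.06.

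| p | a | Withdrawn, reminder v control | Observed rates | RR (reversed) |
|---|---|---|---|---|
| 38% | 20% | 10% v 5% | 40.0% v 38.9% | 1.03 (0.97) |
| 38% | 20% | 20% v 10% | 42.5% v 40.0% | 1.06 (0.94) |
| 38% | 20% | 30% v 10% | 45.7% v 40.0% | 1.14 (0.88) |
| 38% | 30% | 20% v 10% | 40.0% v 38.9% | 1.03 (0.97) |
| 38% | 38% | any | 38% v 38% | 1.00 |
| 20.9% | 20% | 20% v 10% | 21.1% v 21.0% | 1.01 (0.99) |
| 20.9% | 10% | 20% v 10% | 23.6% v 22.1% | 1.07 (0.94) |

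Equal rates do not guarantee safety. With 20% withdrawn in both arms but a = 20% in one and 30% in the other, at p = 38%, the rates are 42.5% v 40.0%, again RR 1.06 (0.94 reversed).

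**Type I error** (p = 38%, 300 per arm, no design effect, nominal two-sided 5%). With a = 20%: about 6% for 10% v 5%, 9% for 20% v 10%, and 13% for 20% v 5%. With a = 10% and 20% v 5%: about 25%.

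**Pooled GEE.** Section 12.2.2 also plans GEE over baseline and months 3, 6 and 12. The plan does not fix the specification, so I assume independence working correlation and an arm term only. If those withdrawn contribute k of four visits:

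rate = [4(p − f·a) + k·f·a] / [4(1 − f) + k·f]

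With p = 0.38 and a = 0.20, withdrawal after month 3 (k = 2) gives 0.4000/0.3895 = 1.03 for 20% v 10% and 0.4118/0.3895 = 1.06 for 30% v 10%. Withdrawal after month 6 (k = 3) gives 0.3895/0.3846 = 1.01 and 0.3946/0.3846 = 1.03. An arm-by-time model would differ.

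**Balanced withdrawal with a true effect.** Suppose a gain of 10 points in accessors and none in non-accessors, with non-access f and a share s of non-accessors withdrawn. The effect in all randomised is 10(1 − f). Among those remaining it is 10(1 − f)/[(1 − f) + f(1 − s)]. If all are withdrawn (s = 1), this is 10 v 9 points at f = 10% and 10 v 8 at f = 20%. If half are withdrawn, it is 9.5 v 9 and 8.9 v 8.

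**The case against.** The case for leaving this alone has real content.

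- **Exposure is shared.** Controls also receive SMS and the combined arm receives both formats, so there is no obvious format-based reason for text and control to differ. A read receipt records opening, not comprehension, so low literacy need not register as non-access. The plan describes the graphics as suitable for basic phones. This weakens the case for a large imbalance, especially text v control, but leaves graphic v text open.
- **Discretion is blinded.** Section 7.1 says "The participants will be aware of the intervention status, but the researcher and clinical staff will not", and section 9.2.5 blinds the data manager to participant details. If that holds, staff cannot steer withdrawals by arm. It does not equalise real differences in access between message types.
- **Non-access should be uncommon.** Phone access is an entry condition, it is checked by call (sections 8.5 and 9.2.3), and problems are addressed at visits (section 5.2). The 30% v 10% case, applied to all three reminder arms, implies (3 × 30 + 10)/4 = 25% overall, above the 20% loss in section 12.1. It is best read as an extreme; 20% v 10% implies (3 × 20 + 10)/4 = 17.5%.
- **The distortion may be small.** Data before withdrawal stay usable, the pooled analysis dilutes the shift, and no passage names month 12 as the primary timepoint.
- **Intent.** Section 9.3 justifies the 12-month follow-up by high exposure and proof of concept, which suits an effect in those reached. That purpose can be served by the per-protocol set without discarding outcomes.
- **Missed visits.** Withdrawal and loss to follow-up are different statuses and can coexist. This is fair: the second point is a gap to close, not a contradiction.

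These points limit likelihood and size. None supplies the missing outcomes.

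**Conclusion.** The concern holds. The plan contains a rule that lets a post-randomisation event, possibly related to the assigned message, end study participation, with no provision for outcomes afterwards. Neither the named analysis sets nor the attrition allowance repairs this.

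Size and direction cannot be derived from the documents, because non-access rates and adherence in those withdrawn are not given and the rule is discretionary. Under the assumed rates with no true effect, the month-12 RR is 1.00 to 1.07 (or 0.94 to 1.00 reversed) for imbalances up to 20% v 10%, and about 1.14 (0.88) in the extreme case at 38% adherence. Shifts in the assumed pooled analysis are 1.01 to 1.06. These are modest beside the 50% improvement the trial is designed to detect, but they can matter for the text v graphic comparison, where smaller differences may be at issue. The change should be made because it is cheap and because outcomes not collected cannot be recovered later.

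**What to change.** In section 13.3 (Withdrawal of Study Participants):

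1. Delete not accessing SMS as a ground for withdrawal from the study. Record it as non-receipt of the intervention.
2. Keep inviting these participants to every remaining scheduled visit, including month 12, unless they withdraw consent or are lost under the section 9.3 rule.
3. In section 12.2.2, analyse them as randomised in the intention-to-treat analysis, use message access only to define the per-protocol set, and report non-access and withdrawal by arm.
4. Secondarily, reconcile the missed-visits ground with section 9.3, so that a reachable participant who missed months 3 and 6 is still invited at month 12.

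A single sentence stating that follow-up continues after messaging stops would meet the core need, but it would leave the withdrawal ground in place to be misread.

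The cost is a protocol amendment, presumably reviewed by the bodies listed in section 16.0, plus some additional tracing, reimbursement and assays (sections 9.3, 16.3 and 19.1) within visits already scheduled. The estimated effect may be smaller, because non-accessors stay in the comparison.

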13.3 Direct access to source data/documents

The regulatory agency, and other authorised representatives of the sponsor will have direct access to source documents to permit trial related monitoring and audits.

13.4 Quality control and quality assurance

The quality assurance manager at the trial site will conduct internal audits to check that the trial is being conducted, data is being recorded, analysed, and accurately reported according to the protocol, trial SOPs, and in compliance with ICH GCP. The audits will also include laboratory activities for the collected blood samples according to an agreed audit schedule. The Clinical Trials and Research Governance Office in Oxford may carry out an audit to ensure compliance with the protocol, GCP and appropriate regulations.

13.5 Trial Registration and Monitoring

The trial will be registered on the clinical trial registry before participant enrolment into the study. The trial will be monitored as a behavioural intervention by the monitoring department of the Clinical Trials Facility (CTF) at KEMRI-Wellcome Trust Research Programme (KWTRP). Regular monitoring will be performed according to International Council for Harmonisation (ICH) Good Clinical Practice (GCP) and a Monitoring Plan. Monitors will check whether the clinical trial is conducted, and data are generated, documented, and reported in compliance with the protocol, GCP and the applicable regulatory requirements.

14.0 INTELLECTUAL PROPERTY

Any intellectual property rights that arise from the work will be safeguarded according to the current KEMRI guidelines and the Industrial Property Act of 2001, sections 32, 58 and 80 and

APHRC guidelines. The scientific and intellectual contributions of all persons involved in the research will be appropriately acknowledged in all publications and presentations arising from the work.

15.0 TIME FRAME/DURATION OF THE TRIAL

Activities	2022		2023				2024	
	Q3	Q4	Q1	Q2	Q3	Q4	Q1	
Protocol development and internal review	■	■						
Engagement with the Kilifi and Nairobi County Department of Health and the SMS company	■	■	■	■	■			
Ethical board reviews (SERU, PPB, NaCOSTI, OxTREC) and trial registration			■	■				
Pre-study focus groups and community engagement				■	■			
Audit of phone ownership and ASM availability, enrolment, and randomisation				■	■			
Roll out the SMS trial: sample collection and assessment					■	■	■	■
Data cleaning, entry, and analysis					■	■	■	■
Report writing and close out								■

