Intervention(s)	
This will be a behavioural intervention with no investigational medicinal product. The intervention will be a mobile messaging service that sends short messaging service (SMS) as texts or graphics to people with epilepsy to remind them to take their medication and to refill their prescription and educational messages to share important messages tackling stigma and tips to improve quality of life
 
We will also engage peripheral health facilities where PWE participating in the study go for ASM refills, in collaboration with the respective county departments of health, to maintain adequate supply of anti-seizure medications through:
 
 i. ongoing capacity building studies in Kilifi such as the mental health Gap Action Programme-Intervention Guide (mhGAP-IG) training which is empowering primary healthcare providers at peripheral health facilities to identify and manage epilepsy and other mental health disorders ii. supporting healthcare providers at peripheral facilities through in-person visits, if the COVID-19 situation, permits or by telephone or standard message reminders to restock their ASM supply 
The participants in the no-intervention group will receive “placebo” health messages not related to epilepsy such as use of bednets.

	
The SMS reminders will be sent at a frequency that will be agreed upon during pre-study engagements with potential participants, whether daily, weekly, or monthly. The participants will be able to respond to these texts to report on their health status and any adverse events.
 
To evaluate whether SMS reminders improve adherence, we will use:
 
 i. Self-reporting adherence scales- the Morisky Medication Adherence Scale (MMAS-8) ii. Measurement of ASM plasma levels at 3, 6 and 12 months from baseline.
Trial Duration	
Each individual participant's participation will take 12 months.
 
The trial itself will last up to three years to account for:
 
 i. different enrolment timepoints of participants ii. analyses, close out and dissemination of findings
Safety Evaluation	
This trial doesn't involve administration of medicinal products.
 
No adverse events are expected in relation to administration of message reminders.
 
However, we will document any ASM-related adverse events as part of routine pharmacovigilance in the care of PWE.

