We will send out reminders to some participants either as a text, a picture, or both a text and a picture to remind them to take their medication. In addition, we will also engage staff at peripheral health facilities where the PWE go for medication refills through ongoing capacity building of all healthcare providers in public health facilities in Kilifi County on management of epilepsy and direct engagement of the respective county Departments of Health to ensure sustained supply and availability of drugs for managing epilepsy. We will ask participants questions regarding how they take their medications, their quality of life and stigmatising experiences before and after they have received message reminders. These sessions will take about 3 hours, including breaks and time spent for clarification and obtaining samples. All study activities will take place at KWTRP in Kilifi and APHRC in Nairobi. Messages will be sent throughout the 12 months for each individual participant and assessment of adherence, quality of life and stigma will be done at the first visit and subsequent follow up visits at 3, 6 and 12 months into the study. To confirm self-reported adherence, we will also collect blood

samples of not more than 5 ml from participants and compare the concentration of antiseizure medications before and after they have received message reminders. Blood samples will be collected at the clinics during the first visit and subsequent follow up visits. All the samples will be stored at KWTRP Main Laboratory and analyses will be conducted at the end of the study at the CREATES Laboratory (<https://creates.strathmore.edu/>) hosted by Strathmore University. Clinicians attending to PWE in the study will continue to advice all participants on the need for adhering to their medication for good outcomes as part of routine care.

What are the benefits and risks/costs of the study for those involved?

Benefits:

If message reminders are found to be useful, they will help in improving adherence outcomes and quality of life among people with epilepsy while reducing misperceptions about epilepsy and stigma experienced by these people.

Risks:

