9.2.6. Procedures

(i) Clinical evaluation, assessment of stigma scores and measures of quality of life

During the baseline visit, information regarding epilepsy factors including seizure semiology, electroencephalography (EEG) and medical co-morbidities as well as sociodemographic characteristic will be assessed using tools that have been validated in this setting. Comprehensive clinical examination, and assessment of self-reported sigma and measures of quality of life and collection of blood samples will also be conducted at the baseline visit. Stigma scores will be assessed using standardized Kilifi Epilepsy Stigma Scale and while quality of life will be assessed using the World Health Organization Quality of Life Scale (WHOQOL-BREF). These tools will be validated for the Nairobi site prior to administration.

(ii) Measurement of adherence

Information on adherence to ASMs will also be collected using a validated self-reporting tool, the Morisky Medication Adherence Scale (MMAS-8) and validated using blood samples. Blood will be drawn (not exceeding 5mls) to measure detectable and optimal plasma levels of ASMs at baseline and during three follow up timepoints; at three months, six months and at 12 months (table 1). Optimal and detectable levels of ASMs in blood. All assays for ASMs will be done at the end of the study using a TDxFx analyser and automated VitaLab Selectra E Clinical Chemistry (Abbott Laboratories, Abbott Park, IL, USA) at Centre for Research in Therapeutic Sciences (CREATEs), Strathmore University.

(iii) Short message service (SMS) intervention

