9.3 Follow-up Visit(s) and End of Treatment Visit

Participants will be invited to the study clinics for follow up visits to examine adherence to anti-seizure medications and assess their quality of life and stigma scores three, six and twelve months from the first visit. The long follow up period per individual of 12 months is selected to ensure high exposure to the intervention to show proof of concept. All other routine clinical assessments will be done during this follow up visit including physical examination, EEG recordings and medication refill. Participants who fail to show up for scheduled follow up visits will be contacted by telephone up to three times and if unsuccessful, followed up at home to remind them to come for their scheduled visits. Participants who are not reached after 3 telephone calls and one home visit will be considered lost to follow up.

Table 1: Study Schedule

	Screening visit 1	Pre-enrolment screening call	Randomisation visit 2 at baseline	Follow up visits 1	Follow up visits 2	End of intervention
Study Month	Use available data	-1 week	0	3	6	12
Assessment / Procedure						
Provide Patient Information Sheet and Informed Consent Form and/or Assent Form	x					
Obtain written informed consent and/or assent	x					
Call to check phone availability/accessibility		x				
Demography	x					
Medical history	x					
Physical examination	x		x	x	x	x
Vital statistics e.g., heart rate and blood pressure	x		x	x	x	x
12-lead EEG	x					x
Blood for adherence levels	x		x	x	x	x
Morisky self-reported scale	x		x	x	x	x
Stigma scores scale	x		x	x	x	x
Quality of life scale			x	x	x	x

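### The section 15 time chart appears to end sampling one quarter before participants enrolled in 2023 Q3 reach month 12, which conflicts with the planned 12-month follow-up.

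*Combined protocol and SAP*

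**What the plan says.** **Follow-up per participant.** The synopsis (1.4) states: "Each individual participant's participation will take 12 months". The lay summary (2.0) says: "Messages will be sent throughout the 12 months for each individual participant". Section 9.2.6 schedules blood sampling "at baseline and during three follow up timepoints; at three months, six months and at 12 months". Section 9.3 counts visits from each person's own start: "three, six and twelve months from the first visit". Table 1 places the end of the intervention at month 12.

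**Overall duration.** The synopsis says "The trial itself will last up to three years to account for" staggered enrolment, and then analysis, close-out and dissemination. The lay summary gives an initial three years from the date of approvals, with renewal possible.

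**Section 15 chart.** The chart has eight columns: two under 2022, four under 2023 and two under 2024.
- "Audit of phone ownership and ASM availability, enrolment, and randomisation" fills the 2023 Q2 and Q3 columns.
- "Roll out the SMS trial: sample collection and assessment" fills four columns, from 2023 Q3 to the last one.
- Report writing and close-out fill the last column only.

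The first 2024 column is labelled Q1. The second has no quarter label in the copy read.

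**The concern.** A chart that enrols over two quarters must keep collecting data until 12 months after the second of them ends. This one seems to stop earlier, and it puts close-out in the same column as the last sampling, although section 9.2.6 leaves all drug-level assays to the end of the study.

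What is at stake is the month-12 visit. Section 9.3 justifies the 12-month period by the need for high exposure to the intervention, and month 12 is the only visit at which that exposure is complete. Section 12.2.2 plans a comparison at each visit as well as a model over all visits. If staff worked to the chart, the month-12 comparison would rest on the earlier enrolees only.

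**Working it through.** **1. Inputs.** Enrolment window: 1 April to 30 September 2023 (section 15). Follow-up: 12 months from the first visit (1.4, 9.3). End of the sampling row: 30 June 2024, if the unlabelled column is 2024 Q2. Size: 300 per arm, 1,200 per site (12.1). The documents give no accrual rate.

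**2. Month-12 dates.** Month-12 date = enrolment date + 12 months.
- Enrolled 1 April to 30 June 2023: month 12 falls 1 April to 30 June 2024, inside the row.
- Enrolled 1 July to 30 September 2023: month 12 falls 1 July to 30 September 2024, entirely after the row. These participants have between 9 and just under 12 months observable.
- The latest enrolee reaches month 6 at the end of March 2024, so months 3 and 6 are attainable for everyone.

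**3. Shortfall.** April 2023 to September 2024 is six quarters. The chart covers 2023 Q2 (enrolment, with baseline assessments under 9.2.4) to 2024 Q2, which is five. The gap is 6 − 5 = 1 quarter.

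**4. Share without a month-12 visit, if conduct followed the chart.**

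| Assumption | Share missed |
|---|---|
| Even accrual by day: 92 of 183 days | 50.3% (about 150 of 300 per arm, 600 of 1,200 per site) |
| One quarter of participants enrol in 2023 Q3 | 25% |
| Three quarters enrol in 2023 Q3 | 75% |
| Baseline starts only with the roll-out row (1 July 2023) | nearly all |
| Last column runs to 2024 Q3 or later | 0% |

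**5. Room in the stated duration.** The chart spans 8 quarters (24 months). Sampling to 2024 Q3 makes 9 quarters (27 months) from 2022 Q3, against an allowance of 36 months.

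**6. Scale for a month-12 comparison.** Table 2 first. Take 30% v 50% adherence, two-sided 5% (assumed) and 95% power, with n = [1.960·√(2·0.4·0.6) + 1.645·√(0.3·0.7 + 0.5·0.5)]² / 0.2² = 153. Multiplying by 1.5 (design effect) and 1.1 (attrition) gives 252.45, rounded up to the stated 253. On that basis, the power of one pairwise month-12 comparison at one site is:

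| Rates and allowances | 300 per arm | 150 per arm |
|---|---|---|
| 30% v 50%, n/1.5 (no further dropout) | 98.5% | 82.8% |
| 30% v 50%, n/1.65 (attrition included) | 97.6% | 79.1% |
| 38% v 50%, n/1.5 (38% = 100% − the 62% gap in 12.1) | 67.8% | 40.0% |

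These figures cover only that cross-section. Power for the repeated-measures model was not calculated.

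**The case against.** The best defence is that the chart is a forecast and the operative text is sound. No section ends follow-up on a calendar date. Sections 1.4, 2.0 and 9.3 tie it to the individual, the three years exist partly because people enrol at different times, and the lay summary starts the study when approvals arrive. This stands, and it defeats the inference a reader might draw that half the month-12 outcomes will be lost. Loss follows only if staff apply the chart against the rest of the protocol. The defence does not correct the chart, which plans 24 months with close-out in the last quarter, and nothing says which statement governs.

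The end date also rests on an unlabelled column. That is a fair limit. Consecutive quarters make it 2024 Q2, but a column reaching 2024 Q3 would remove the problem.

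A reader might count six quarters needed against the four in the roll-out row and infer a two-quarter gap. That omits the enrolment and baseline quarter, 2023 Q2. If data collection instead began only in 2023 Q3, five quarters would be needed and four given. Either way the gap is one quarter.

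Finally, no visit is named as primary, and the generalised estimating equations use baseline and months 3, 6 and 12. A reader should not carry the power drop above over to the main adherence analysis, most of whose data would survive.

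On the other side, ethics review and registration extend into 2023 Q2, and section 13.5 requires registration before enrolment. That tends to push accrual towards Q3, although the documents do not settle it.

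**Conclusion.** The point holds as a conflict between section 15 and the 12-month follow-up. On the natural reading, the chart is one quarter short, and nobody enrolled in 2023 Q3 can have a month-12 visit before sampling and close-out end. The figure of about 50% needs even accrual and a last column equal to 2024 Q2; the range in the working runs from none to nearly all. The effect is confined to month 12 and depends on conduct following the chart. The documents do not support a firm forecast of lost outcomes or a fault in the 12-month design itself. It is a planning inconsistency that is worth correcting because it is cheap to correct and the month-12 visit carries the full exposure.

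**What to change.** Amend section 15:
- Extend the sampling and assessment row to the month-12 visit of the last randomised participant, at least 2024 Q3 if enrolment ends in 2023 Q3.
- Place the end-of-study assays, database lock, final analysis and close-out after that visit.
- Confirm which quarter the last column represents, and reconcile the chart with the three-year duration in the synopsis and lay summary.

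Section 9.3 needs no new wording, because its visits already count from the first visit.

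The cost is an amendment to the time frame and results one or two quarters later. It adds no participants or procedures and stays inside the stated three years.
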